5.4. PET/CT scan

- 5.4.1. **Scan coverage.** Scan coverage will extend from mid-thigh to the base of the skull, starting from the mid-thighs to minimize urinary bladder radiotracer accumulation at the start of PET imaging. Subject to void immediately prior to imaging.
- 5.4.2. **Bed position.** Scan time will be dependent on scanner capabilities. At a minimum, 3 minutes per bed position will be used.
- 5.4.3. **Discharge.** Subject must be monitored for adverse events for a minimum of 2 hours post-injection.
- 5.4.4. **Local Analysis.** A board-certified nuclear medicine physician on-site will interpret the images within 3 business days of the imaging study. These interpretations will not be used for final evaluation, however regional positivity results will be collected as study data.
- 5.4.5. **Internal Blinded Reads.** Imaging data will be interpreted by two different readers in a random order at separate reading sessions. Cross sectional imaging from the CT will be available for anatomic correlate. Final reads for each subject will be interpreted as positive or negative for the presence of pelvic nodal disease, and positive or negative for the presence of osseous metastatic disease and soft tissue metastases outside of the pelvis. All readers will have undergone ⁶⁸Ga PSMA PET training.
- 5.4.6. **Results dissemination.** Local analysis will be shared with the subject's

clinician and will be included in the subject's medical record.

5.5. **Visual Interpretation of PET data (internal blind reads)**

Regions of suspected disease will be graded on a two-point scale by each reader (0=Negative or 1=Positive). A region will be judged as positive if at least one lesion in this region is visually positive. Regions are defined in Table 12.1 in Section 12. Criteria for visual interpretation positive for disease are detailed in Section 12.1.1.

5.6. **Follow-up imaging**

All subjects should be followed as per standard of care consistent with the institution/physician. Reports and copies of any conventional imaging obtained during the 12 month window following the PSMA-HBED-CC PET/CT scan will be obtained. Clinical notes will also be reviewed to identify metastatic lesions. Interpretation of follow-up imaging is performed by local institution following standard procedures. Preferable comparison imaging would be the same imaging device as the initial re-staging work-up as per RECIST guidelines.

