12. EFFICACY ASSESSMENTS

Determination of efficacy requires two primary assessments.

The first assessment is the clinical read of the ^{68}Ga -PSMA-HBED-CC PET/CT scan. Trained readers will identify lesions positive for prostate cancer disease, and based on these results, will categorize specifically defined anatomical regions of the subject (Table 12.2) as positive for disease by ^{68}Ga -PSMA-HBED-CC PET/CT. Criteria are described in Section 12.1 below.

The second assessment is the reference standard determination of disease positivity or negativity also performed on the same specifically defined anatomical regions (Table 12.2). The reference standard definitions are described below, and consist of a combination of pathological confirmation, conventional imaging follow-up evidence, and serial PSA measurements. Criteria are described in Section 12.2 below.

For purposes of endpoints, four major regions are identified for final analysis as defined in Table 12.1. Each region is divided into subregions as defined in Table 12.2. All primary data from ^{68}Ga -PSMA-HBED-CC PET interpretations, pathology results, and conventional imaging results, will be collected per the subregions defined below. The final region assignments and results will be derived from the subregion data as applicable.

Region	Description
1	Prostate Bed
2	Pelvis outside of prostate bed including lymph nodes
3	Extrapelvic soft tissue, lymph nodes and organ metastases (non-bone)
4	Bone metastases

Table 12-1. Major Analysis Regions

Region 2: Pelvis outside of prostate bed	Region 3: Extrapelvic soft tissue	Region 4: Bone metastases
Right obturator	Lung	Spine
Left obturator	Liver	Ribs
Right external iliac	Pancreas	Pelvis
Left external iliac	Spleen	Extremities
Right internal iliac	Intestine	Skull
Left internal iliac	Mesentary	Sternum
Other pelvic regions	Brain	Clavicle
	Other soft tissue	Other bone
	Abdominal nodes	
	Thoracic nodes	
	Other nodes	

Table 12-2. Subregion Classification

12.1. **^{68}Ga -PSMA-HBED-CC PET Results Definition**

Imaging interpretation ^{68}Ga -PSMA-HBED-CC PET:

Local Interpretations: PET images will initially be interpreted by a board certified nuclear medicine physician or a board-certified radiologist experienced in reading PET at the time of the imaging study at the institution that the study is being performed. These interpretations will not be used for evaluation of the primary endpoint.

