12.1.1.3. Bone lesions will be considered positive if the ^{68}Ga -PSMA-

HBED-CC uptake is focal and greater than physiologic bone marrow.

- Bone lesions will be classified by further by region: spine, ribs, pelvis, extremities, skull, sternum, and clavicle, as Defined in Table 12.2. These sub-regions will be correlated with reference standard results in these sub-regions, however this sub-region data will not be directly used for evaluation of the primary or secondary endpoints, but for exploratory analysis.

12.1.1.4. Prostate bed and prostate lesions will be considered positive if the ⁶⁸Ga-PSMA-HBED-CC uptake is focal and greater than physiologic background activity of the involvement organ or anatomic site.

12.2. Reference standard definition:

12.2.1. Histopathology/Biopsy will be the primary determinate of tissue positivity and negativity for prostate cancer disease. Pathology date, organ, and location as well as any notes related to the pathology will be obtained from the subject chart. The anatomical region/sub-region the pathology occurred in will be assigned by the investigator team:

⁶⁸Ga-PSMA-HBED-CC positive findings are aimed to be confirmed by histopathology/biopsy if clinically feasible. Pathology performed 60 days before or after the ⁶⁸Ga-PSMA-HBED-CC PET will be available for correlation.

Histopathological procedures and biopsies will be performed as clinically indicated and as per institutional protocol.

12.2.1.1. Lymph Nodes, Visceral Lesions, and Bone Lesions positive for disease by pathology.

- Lesions with positive pathologic confirmation will be regarded as positive for disease. The regionality of the resected tissue will be assigned into respective regions and sub-regions as described above in Table 12.2.

12.2.1.2. Lymph Nodes and Visceral Lesions negative for disease by pathology.

- Tissue removed and negative for pathology are considered negative for prostate cancer disease, unless subsequent conventional imaging or ⁶⁸Ga-PSMA-HBED-CC PET imaging demonstrates that targeted tissue were not resected. In this case:

- i. Subjects can be rescanned with dedicated CT, MRI, or ⁶⁸Ga-PSMA-HBED-CC PET/CT to determine if the suspicious ⁶⁸Ga-PSMA-HBED-CC tissue was removed. If the tissue is confirmed as removed, this is considered negative for disease.

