- Regions with no lymph nodes determined to be positive by the conventional imaging criteria described above and without pathology will be designated regions indeterminate for prostate cancer disease.
- Subjects that have had neither pathology sampling, nor conventional imaging follow up will have all regions designated as indeterminate for disease by reference standard.

12.2.2.2. Visceral lesions (non-lymph node soft tissue or organ) and prostate bed and prostate lesions will be assessed by change in size.

i. Positive for disease:

- a. For subjects undergoing systemic treatment (alone or in combination with targeted treatment): If on post-treatment follow-up imaging within 3-12 months, visually conspicuous lesions seen on CT or MRI decrease by more than 30% in long axis diameter and PSA declines by more than 50%.
 - If PSA increases by more than 25% (PCWG3 definition of recurrence) on systemic therapy, then an increase in the size of lesion by more than 20% in the long axis diameter will be considered positive for disease.
- b. In subjects with localized suspected lesions(s) receiving targeted treatment without concomitant systemic treatment there are two ways to meet positive disease criteria:
 - If the subject demonstrates a decrease of PSA by greater than 50% after targeted treatment [*OR*]
 - If on post-treatment follow-up imaging within 3-12 months, lesions seen on CT or MRI decrease by more than 30% in long axis diameter (with a minimum of 3 mm in change in size)
- c. For untreated subjects: If on follow-up imaging within 3-12 months, lesions seen on CT or MRI increase by more than 20%

in long axis diameter (with a minimum of 3 mm in change in size).

ii. Negative for disease:

- Conventional Imaging follow up will not be used for assessment of negativity for disease

iii. Indeterminate for disease

- Regions with no visceral lesions determined to be positive by the conventional imaging criteria described above and without pathology will be designated as visceral regions indeterminate for prostate cancer disease.
- Prostate bed and prostate regions not determined to be positive by the conventional imaging criteria described above and without pathology will be designated as prostate regions indeterminate for prostate cancer disease.
- Subjects that have had neither pathology sampling, nor conventional imaging follow up will have all prostate and visceral regions designated as indeterminate for disease by reference standard.

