13.3. Definitions of ^{68}Ga PSMA-HBED-CC accuracy

13.3.1. True positive definitions

13.3.1.1. **^{68}Ga PSMA-HBED-CC PET/CT positive for nodal metastases by internal blind reader** – and pathology (if available) positive for that node, or node positive for disease by imaging as defined in Section 12.2.2.1 If this criteria is met, the subject is defined as true positive for nodal disease.

13.3.1.2. **^{68}Ga PSMA-HBED-CC PET/CT positive for visceral metastases by internal blind reader** – and pathology (if available) positive for that visceral lesion, or, visceral lesion positive for disease by imaging as defined in Section 12.2.2.2. If this criteria is met, the subject is defined as true positive for visceral disease.

13.3.1.3. **^{68}Ga PSMA-HBED-CC PET/CT positive for osseous**

metastases by internal blind reader - and pathology (if available) positive for that osseous lesion, or, osseous lesion positive for disease by imaging as defined in Section 12.2.2.3. If this criteria is met, the subject is defined as true positive for osseous disease.

13.3.1.4. A single nodal, visceral, or osseous region determined as true positive as defined above is sufficient to define the subject as true positive by ⁶⁸Ga PSMA-HBED-CC PET/CT.

13.3.2. **True negative definitions**

13.3.2.1. **⁶⁸Ga PSMA-HBED-CC PET/CT negative for nodal metastases by internal blind reader** – and pathology (if available) negative for disease, and, extra-pelvic node not positive for disease by imaging. If this criteria is met, the subject is defined as true negative for nodal disease.

13.3.2.2. **⁶⁸Ga PSMA-HBED-CC PET/CT negative for visceral metastases by internal blind reader** – and pathology (if available) negative for disease, and, visceral lesion not positive for disease by imaging. If this criteria is met, the subject is defined as true negative for visceral disease.

13.3.2.3. **⁶⁸Ga PSMA-HBED-CC PET/CT negative for osseous metastases by internal blind reader** - and pathology (if available) negative for disease, and, osseous lesion not positive for disease by imaging. If this criteria is met, the subject is defined as true negative for osseous disease.

13.3.3. **False positive definitions:**

13.3.3.1. **⁶⁸Ga PSMA-HBED-CC PET/CT positive for nodal metastases by internal blind reader**, pathology (if available) is negative, and imaging demonstrates that node is not positive for disease. If this criteria is met, the subject is defined as false positive for nodal disease.

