13.3.3.2. **⁶⁸Ga PSMA-HBED-CC PET/CT positive for nodal metastases by internal blind reader**, but pathology (if available) is positive for node but in a different nodal region than the node seen on PSMA PET. If this criteria is met, the subject is defined as false positive for nodal disease.

13.3.3.3. **⁶⁸Ga PSMA-HBED-CC PET/CT positive for visceral lesion by internal blind reader**, pathology (if available) is negative, and imaging demonstrates that the visceral lesion is not positive for disease. If this criteria is met, the subject is defined as false positive for visceral disease.

13.3.3.4. **⁶⁸Ga PSMA-HBED-CC PET/CT positive for visceral lesion by internal blind reader**, but pathology (if available) is positive for visceral lesion but in a different region than the visceral

region seen on PSMA PET. If this criteria is met, the subject is defined as false positive for visceral disease.

- 13.3.3.5. **^{68}Ga PSMA-HBED-CC PET/CT positive for osseous lesion by internal blind reader**, pathology (if available) is negative, and imaging demonstrates that the osseous lesion is not positive for disease. If this criteria is met, the subject is defined as false positive for osseous disease.
- 13.3.3.6. **^{68}Ga PSMA-HBED-CC PET/CT positive for osseous lesion by internal blind reader**, but pathology (if available) is positive for osseous lesion but in a different region than the osseous region seen on PSMA PET. If this criteria is met, the subject is defined as false positive for osseous disease.
- 13.3.3.7. A subject is defined as false positive for disease by ^{68}Ga PSMA-HBED-CC PET/CT if one or more regions as defined above are defined as false positive regions and the subject is not defined as true positive as defined in Section 13.3.1

13.3.4. **False negative definitions:**

- 13.3.4.1. **^{68}Ga PSMA-HBED-CC PET/CT negative for nodal metastases by internal blind reader**, and pathology (if available) positive for any node or positive for disease by imaging as defined in Section 12.2.2.1. If this criteria is met, the subject is defined as false negative for nodal disease.
- 13.3.4.2. **^{68}Ga PSMA-HBED-CC PET/CT negative for visceral lesion by internal blind reader**, and pathology (if available) positive for any visceral lesion, or, visceral lesion positive for disease by imaging as defined in Section 12.2.2.2. If this criteria is met, the subject is defined as false negative for visceral disease

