- 13.3.4.3. **^{68}Ga PSMA-HBED-CC PET/CT negative for osseous lesion by internal blind reader**, and pathology (if available) positive for any osseous lesion, or, osseous lesion positive for disease by imaging as defined in Section 12.2.2.3. If this criteria is met, the subject is defined as false negative for osseous disease.
- 13.3.4.4. A subject is defined as false negative for disease by ^{68}Ga PSMA-HBED-CC PET/CT if the subject is negative for disease in all regions by ^{68}Ga PSMA-HBED-CC PET/CT, but positive for disease by pathology or follow-up imaging in any region.

13.3.5. **Non-evaluable definitions:**

- 13.3.5.1. Any region that does not have sufficient data to meet the criteria for definition of true positive region, true negative region, false positive region, or false negative region will be classified as non-evaluable.
- 13.3.5.2. Any region that does not have sufficient data to meet the

criteria for definition of true positive subject, true negative subject, false positive subject, or false negative subject will be classified as non-evaluable.

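### Section 13.3 has no scoring rule for the prostate bed: a detected local-only recurrence cannot be a true positive, but a missed one is a false negative, so the primary sensitivity can be understated

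*Combined protocol and SAP*

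**What the plan says.** Section 12 states: "For purposes of endpoints, four major regions are identified for final analysis as defined in Table 12.1". Region 1 in that table is the prostate bed. It is separate from Region 2 (the rest of the pelvis), Region 3 (extrapelvic soft tissue, nodes and organs) and Region 4 (bone).

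The bed has its own PET criterion in 12.1.1.4, which opens "Prostate bed and prostate lesions will be considered positive if the" and is listed apart from the visceral criterion in 12.1.1.2. It also has an imaging reference criterion in 12.2.2.2: "Visceral lesions (non-lymph node soft tissue or organ) and prostate bed and prostate lesions will be assessed by change in size".

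Section 13.3 turns these reads into true and false positives and negatives. Its region-level rules cover nodal, visceral and osseous disease only. At subject level:

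- **True positive (13.3.1.4):** "A single nodal, visceral, or osseous region determined as true positive as defined above is sufficient to define the subject as true positive".
- **False positive (13.3.3.7):** one or more of the regions defined there "are defined as false positive regions and the subject is not defined as true positive as defined in Section 13.3.1".
- **False negative (13.3.4.4):** PET negative in all regions, "but positive for disease by pathology or follow-up imaging in any region".
- **Non-evaluable (13.3.5):** insufficient data for any of the other classes.

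The final-read description in 5.4.5 begins "Final reads for each subject will be interpreted as positive or negative for the presence of pelvic nodal disease" and goes on to bone and to soft tissue outside the pelvis. It has no prostate-bed category.

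**The concern.** Sensitivity needs its true positives and false negatives to be counted over the same sites. Here the numerator can be reached only through nodal, visceral or osseous disease, while the false-negative rule takes in every region, and Table 12-1 makes the bed one of those.

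The population is men with biochemical recurrence after prostatectomy or radiation, so recurrence confined to the bed is a case the rules must handle. Per-subject sensitivity is the primary endpoint, and Section 13.1 says the pilot will inform the sensitivity used to power a larger study. A scoring asymmetry would carry into that figure. The per-region PPV, a secondary endpoint, has no defined numerator or denominator for Region 1.

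**Working it through.** **1. Four records scored by Section 13.3 as written**

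| Record | Rule reached | Class |
|---|---|---|
| A. PET positive only in the bed; bed biopsy positive | Not 13.3.1.4 (no listed class); not 13.3.4.4 (PET is not negative everywhere) | None; non-evaluable by default |
| B. PET negative everywhere; bed biopsy positive | 13.3.4.4 | False negative |
| C. PET positive in the bed (biopsy proven) and in one node that is pathology-negative and not positive on imaging | Node meets 13.3.3.1; subject is not true positive, so 13.3.3.7 | False positive |
| D. PET positive only in the bed; bed biopsy negative | No false-positive rule | None; non-evaluable by default |

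A and B have the same disease, but only the miss is counted. A man who also has a true-positive node, visceral lesion or bone lesion is unaffected.

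**2. The plan's own figures**

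Section 13.1 gives half-widths for n = 30 by the normal approximation, 1.96 × √(p(1−p)/30). For p = 70, 75, 80, 85 and 90% this gives 16.40, 15.49, 14.31, 12.78 and 10.74%, which matches the printed 16.4, 15.5, 14.3, 12.8 and 10.7%.

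**3. Size when all misses are ascertained**

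Sensitivity is taken as TP/(TP+FN). Section 13.1 prints TP/(TP+FP), a separate error. Let s be the sensitivity with the bed scored like the other sites, and f the share of detected men whose only proven disease is in the bed. The documents do not give f; 10% to 40% is assumed. The rules as written remove f of the true positives and keep every false negative:

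sensitivity as written = (1−f)s / [(1−f)s + (1−s)]

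For s = 80% and f = 20%: 0.64/(0.64 + 0.20) = 76.2%.

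| s | f = 10% | 20% | 30% | 40% |
|---|---|---|---|---|
| 70% | 67.7% | 65.1% | 62.0% | 58.3% |
| 80% | 78.3% | 76.2% | 73.7% | 70.6% |
| 90% | 89.0% | 87.8% | 86.3% | 84.4% |

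With 30 reference-positive men and s = 80%, the evaluable count falls from 30 to 27.6, 25.2, 22.8 and 20.4 across these shares. The half-width grows from 14.3% to 15.4, 16.6, 18.1 and 19.8%. Thirty is an upper limit, because the plan has 30 patients in total.

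**4. Dependence on the number of false negatives (whole numbers, Wilson 95% limits where shown)**

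| TP (of which bed-only) | FN | Bed scored on both sides | As written |
|---|---|---|---|
| 24 (8) | 6 | 24/30 = 80.0% (62.7–90.5) | 16/22 = 72.7% (51.8–86.8) |
| 24 (5) | 6 | 24/30 = 80.0% (62.7–90.5) | 19/25 = 76.0% (56.6–88.5) |
| 24 (5) | 1 | 24/25 = 96.0% | 19/20 = 95.0% |
| 24 (8) | 0 | 24/24 = 100% (86.2–100) | 16/16 = 100% (80.6–100) |

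In the first row, if 2 of the 6 false negatives are in the bed and the bed is removed from both sides, the result is 16/20 = 80.0% (58.4–91.9). Either symmetric rule restores the estimate.

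**5. Under the formula as printed**

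With TP/(TP+FP) and 3 false positives, losing 8 bed-only true positives changes 24/27 = 88.9% to 16/19 = 84.2%. Record B does not enter that formula at all, so the detected-versus-missed contrast needs the TP+FN denominator.

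**The case against.** **The bed may be meant to count as visceral.** Sections 13.3.1.2 and 13.3.4.2 judge visceral disease by 12.2.2.2, the section that also holds the bed's imaging reference, and the PET criteria for the two are alike. On that reading A and C become true positives. This is the best counter-argument, but it fails on balance. Section 13.3.1.2 requires a PET read positive for visceral metastases. Section 12.1.1 lists visceral and prostate-bed lesions as separate classes, and 12.2.2.2 gives each its own indeterminate category. Even if it was intended, two analysts could score the same data differently.

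**The target may be metastatic disease only.** The opening of 13.1 says so, and the broad wording of 13.3.4.4 follows three rules that are nodal, visceral and osseous. If regions there means only those three, the rules are symmetric. But objective 1.1.1 speaks of tumor location, 13.1 goes on to identifying biochemical recurrence, and Table 12-1 makes the bed an endpoint region.

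**False negatives will be few.** This stands, and it limits the size. Section 5.6 says they arise only from positive biopsies of PET-negative lesions and calls this uncommon; 12.2.2 limits follow-up imaging to PET-positive subjects. Under-ascertained misses also push sensitivity upward, separately from this point.

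**Non-evaluable is an inference.** This also stands: 13.3.5 is about insufficient data, and record A has a positive biopsy. Strictly he is unclassified. Either way he is neither a true positive nor a false negative.

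**Conclusion.** The point holds in a conditional form. The true-positive and false-negative rules do not cover the same sites, and the text offers no reading that reconciles them consistently. With TP/(TP+FN), sensitivity is lowered whenever some detected men have bed-only disease and there is at least one false negative. The 78.3% to 70.6% range for a true 80% rests on an assumed 10% to 40% bed-only share and on full ascertainment of misses. Given 5.6 and 12.2.2, the realistic effect is probably smaller and may be zero. The loss of proven detections and of evaluable subjects remains even then.

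Three stronger conclusions are not supported:

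- **That scoring alone will take the result below the anticipated 80%.** This needs several false negatives, which the plan makes uncommon.
- **That per-subject PPV is biased downward.** Leaving out A, or scoring C as false positive, lowers it; leaving out D raises it. The net direction is not established.
- **That a detected bed recurrence is itself a false negative because 5.4.5 has no bed category.** Section 5.5 has readers grade the Table 12.1 regions and 12.1.1.4 gives a bed criterion, so he is not PET-negative in all regions.

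It should still be settled before the reads are scored, because it defines the primary endpoint and a choice made afterwards would be post hoc.

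**What to change.** Preferred, because it agrees with Table 12-1 and objective 1.1.1:

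- Add prostate-bed/prostate (Region 1) true-positive, true-negative, false-positive and false-negative rules to 13.3, parallel to the visceral ones and citing 12.1.1.4, pathology and 12.2.2.2.
- Name the prostate bed in 13.3.1.4 as a region sufficient for a true-positive subject.
- Add the prostate bed to the pathology rules in 12.2.1.1 and 12.2.1.2 and to the final read in 5.4.5.

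Alternative, if only metastatic disease is the target: restrict 13.3.4.4 to nodal, visceral and osseous regions and remove Region 1 from the endpoint regions.

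Under either option, correct the denominator printed in 13.1 to TP + FN.

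The cost is wording. No extra scans, readers or patients are needed, since 5.5 and 12.1.1.4 already provide for a bed read; the read form is not in the documents, so check that it records one. The downside of the preferred option is that prostate-bed false positives would enter the PPV denominator. The downside of the alternative is that local recurrence drops out of the primary endpoint altogether.
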